8.1 Adverse Event List for MSOT

A slight, reversible reddening and temperature increase of sensitive skin. All adverse events and expected treatment effects, including mild events, will be monitored throughout the study until discharge.

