8.6 Post-imaging Procedural Events for MSOT

The post-imaging procedural events for MSOT are those events that are expected and standard to post-imaging as for ultrasound and include slight, reversible reddening and temperature increase of sensitive skin for a duration of ≤ 24 hours post-surgery. All unexpected events shall be captured. Post-imaging procedural events that occur in increased frequency and severity over what should normally occur in the medical opinion of the investigator will be considered adverse events (AE). AEs will be reported.

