10.0 Statistical Considerations

10.1 Analysis of Primary Objective

10.1.1 The primary objectives are to estimate the rate of adverse events and measure the skin temperature change following MSOT imaging both pre- and post-surgery. The adverse events will be estimated by grade, type and relatedness. The first analysis will pool all grade 3 unexpected events that are possibly, probably or definitely related to MSOT together and then construct a 95% exact Clopper-Pearson binomial confidence interval for this estimate. Additionally, measurement of skin temperature will be evaluated where skin temperature greater than 44°C will be recorded¹³. A 95% exact Clopper-Pearson binomial confidence interval for the evaluation of skin temperature will be conducted

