Appendix A – Imaging and Tissue Data Collection Form

Study Number: OU-SCC-MSOT PID: 0 1 - _____

Investigator: [name] Surgery Date: ____/____/____

1) Tumor or Lymph Node Assessments:

a) Target tissue

Tumor

Lymph Node

b) Standard of care method of imaging

MRI _____ tumor amount

PET _____ tumor amount

CT _____ tumor amount

Other: _____ tumor amount

c) Did patient receive neoadjuvant therapy?

Yes

No

d) MSOT Image acquired?

Yes

No

e) Was an indicator dye used during surgery?

Yes

[figure not shown]
No

f) If an indicator dye used during surgery, please indicate which dye.

Isosulfan Blue IC Green

2) Location of Imaging

a) Please circle the location of the imaging (below) and provide further description as necessary

[https://anatomyclass123.com /](https://anatomyclass123.com/)

b) Erythema post-MSOT Imaging (RTOG)

i. Time after imaging: (hr: min) _____

ii. Grade (RTOG)

- 0 No erythema present
- 1 Follicular, faint or dull erythema, epilation, dry desquamation, decreased sweating
- 2 Tender or bright erythema, patchy moist desquamation, moderate edema
- 3 Confluent, moist desquamations other than skin folds, pitting, edema
- 4 Ulceration, hemorrhage, necrosis

3) Clinical Pathology Assessment

a) Date or diagnosis (month / year):

b) Positive tumor tissue:

Yes No
 c) For Pancreatic melanoma breast HNSCC ovarian (check one) indicate stage at diagnosis (**TNM classification**):

Tx T0 Tis T1 T2 T3 T4
 Nx N0 N1 N2 N3
 Mx M0 M1

d) Tumor subtype (if applicable) _____

4) Skin temperatures

Pre-Surgery MSOT imaging			
Pre-imaging Skin Temperature (°C)		Time	
Post-imaging Skin Temperature (°C)		Time	

Post-Surgery MSOT imaging			
Pre-imaging Skin Temperature (°C)		Time	
Post-imaging Skin Temperature (°C)		Time	

5) Patient Monitoring (*)please note that patients must be monitored daily for adverse events until discharge). Please answer yes or no if Erythema at grade III or higher or change in skin pigmentation occurs.**

Yes No

_____ Post surgery	_____ 8 day
_____ 1 day	_____ 9 day
_____ 2 day	_____ 10 day
_____ 3 day	_____ 11 day
_____ 4 day	_____ 12 day
_____ 5 day	_____ 13 day
_____ 6 day	_____ 14 day
_____ 7 day	_____ 15 day

Discharge date: _____

6) Adverse event. Please answer yes or no if Erythema at grade III or higher or change in skin pigmentation occurs.

Yes No

If yes, please fill out details below:

_____ Erythema _____ Time _____ Date

_____ Changes in skin pigmentation _____ Date

7) MSOT Scan Times:

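### Sections 8.0/8.1 and 8.6 disagree on whether mild expected reddening is an adverse event, and Appendix A items 5 and 6 ask only about grade III or higher, so AE estimates by grade can omit grade 1-2 reddening

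*Protocol*

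**What the plan says.** - **Definition (Protocol 8.0).** An adverse event is any untoward occurrence or unfavourable, unintended sign, related or not. Each is assessed for severity and causality. Expected effects are not exempted.
- **Expected effects (Protocol 8.1).** The MSOT adverse event list reads "A slight, reversible reddening and temperature increase of sensitive skin". It continues: "All adverse events and expected treatment effects, including mild events, will be monitored throughout the study until discharge".
- **Grading (Protocol 8.2, SAP 7a).** CTCAE v5.0 is the scale. Section 8.2 adds five attribution levels and an expected/unexpected label that refers back to 8.1 and is meant for expedited reporting only.
- **Post-imaging events (Protocol 8.6).** The same reddening and warming, lasting up to 24 hours after surgery, is classed as an expected procedural event. AE status is kept for "Post-imaging procedural events that occur in increased frequency and severity over what should normally occur", as judged by the investigator. The explicit capture instruction in 8.6 covers unexpected events.
- **Form (Protocol Appendix A).** Item 5 (after surgery, then days 1 to 15) and item 6 (the adverse event item) share one prompt: "Please answer yes or no if Erythema at grade III or higher or change in skin pigmentation occurs". Item 2b records post-imaging erythema once, with a time, on the RTOG 0-4 scale. Its grade 1 is "Follicular, faint or dull erythema, epilation, dry desquamation, decreased sweating". Item 4 records skin temperature before and after each imaging session.
- **Analysis (Protocol 10.1, SAP 7a).** "The adverse events will be estimated by grade, type and relatedness". The one pooled AE estimate with an exact interval covers grade 3 unexpected events at least possibly related to MSOT.

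**The concern.** Collecting safety data is the first primary objective, and section 10.1 states the aim as estimating the adverse event rate. Slight reddening is one of only two effects the protocol expects from the device. Whether it reaches the adverse event tables depends on which section the site follows, and 8.6 rests on an individual judgement against a norm that is not given. The prompts most likely to generate an AE entry, items 5 and 6, do not ask about grade 1 or 2 erythema.

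What is at stake is how the mild-event rows are read. An empty row for grade 1-2 skin events could mean that no reddening occurred, or that reddening occurred and was classed as a procedural event. The report could not tell the two apart, and sites or investigators could differ without any of them departing from the protocol.

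**Working it through.** This is mainly a question of data flow, so I traced two cases through the documents and then checked whether any stated figure moves.

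**Case A: faint reddening after imaging, gone within 24 hours.**
1. Under 8.0 and 8.1 it is an adverse event of an expected kind.
2. Under 8.6 it is an expected procedural event, and not an AE unless judged above normal.
3. Items 5 and 6: below grade III, so the answer is no.
4. Item 2b: recordable as RTOG grade 1. There is one time and one grade, although imaging takes place before and after surgery. Items 4 and 7 of the same form do separate the two sessions.
5. REDCap (8.5): receives all AEs. If 8.6 has already denied AE status, nothing is entered, so this route inherits the exclusion.
6. Table by grade, type and relatedness: needs CTCAE grade and attribution. Item 2b supplies neither, and 10.1 and SAP 7a do not mention it.

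Result: the event can be on the form and absent from the AE estimates.

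**Case B: faint reddening still present on day 2.**
1. It now falls outside the 24-hour description in 8.6, so by that section it is no longer the expected event.
2. Item 5 for day 2: below grade III, so the answer is no. There is no grade field for that day.
3. Item 2b has already been used for the post-imaging reading.

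Result: an entry depends on someone raising it unprompted. The form cannot show whether reddening was reversible or stayed within 24 hours.

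**Do the plan's figures change?** The two-sided 95% Clopper-Pearson upper limit is the 0.975 quantile of Beta(x+1, n−x). For x = 0 this is 1 − 0.025^(1/n).
- n = 50: 0 events, 1 − 0.025^(1/50) = 7.11% (plan 7.1%); 4 events, 19.23% (plan: below 20%).
- n = 45: 0, 1, 2, 3 events give 7.87%, 11.77%, 15.15%, 18.27% (plan 7.9%, 11.7%, 15.1%, 18.3%; agreement apart from rounding).

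Mild expected reddening is outside the pooled set on both grade and expectedness. None of these limits moves, whichever section is followed.

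**What a stated tabulation would give.** The documents contain no reddening rate, so these counts are assumptions. With 2, 5, 10 or 20 of 50 patients showing grade 1-2 reddening, the exact 95% intervals would be 0.5-13.7%, 3.3-21.8%, 10.0-33.7% and 26.4-54.8%. With 8.6 applied, the AE table could show 0 in each case.

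**The case against.** The strongest reply is that the effect is recorded. Item 2b is a dedicated field that goes down to faint erythema and has a time, which suits an effect expected to last no more than 24 hours. Item 4 captures the other expected effect, the temperature rise, at all four readings. Section 8.1 requires monitoring of mild events, item 5 itself calls for daily monitoring for adverse events, 8.5 sends all AEs to REDCap, and 9.2.2 provides for study-specific case report forms that may hold CTCAE grade and attribution. Section 8.2 already has an expected category.

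Much of this stands. A reader might infer that Appendix A asks only about grade III or higher, that mild reddening is not captured at all, or that a near-zero headline rate would be an artefact. The documents support none of these. Item 2b grades mild erythema, so affected patients could be found from it, and the pooled estimate excludes mild expected events by definition.

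A reader might also infer that the conflict alters the rule for ending the study at 45 patients with 3 or fewer AEs (10.3.1). That sentence does not restrict AEs by grade. However, it follows directly on a paragraph about unexpected related events of grade 3 or higher and uses the same 20% bound, so I do not rest anything on it.

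What the reply does not answer is the path from item 2b to the analysis. Monitoring is not the same as counting, and 8.6 decides AE status before any REDCap or case report form entry is made. Item 2b also lacks session, attribution, CTCAE grade and a place in the analysis plan.

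**Conclusion.** The point holds as a conflict between sections plus a gap between form and analysis. Sections 8.0 and 8.1 cannot be applied together with 8.6 to mild expected reddening. As written, the estimates by grade, type and relatedness can omit grade 1-2 reddening, and reddening beyond 24 hours has no graded daily field.

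The size is limited. The gap affects the descriptive mild-event rows of a primary safety outcome. It affects no sample size, no stated confidence limit and not the pooled grade 3 unexpected related estimate. The number of events omitted cannot be estimated from the documents; it is zero if reddening does not occur or if sites apply 8.0 and 8.1 rather than 8.6.

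The conclusion assumes that sites follow 8.6 and Appendix A literally, and that no unpublished form asks for skin events of every grade. It should be corrected because the change is cheap and concerns a primary outcome.

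**What to change.** 1. **Reconcile 8.0 and 8.1 with 8.6.** Record expected reddening as an AE labelled expected. The label exists in 8.2 but is limited there to expedited reporting; say that it also applies to recording and analysis, where 10.1 already relies on it.
2. **Items 5 and 6 of Appendix A.** Ask about skin events of any grade, with CTCAE v5.0 term, grade and the 8.2 attribution. Grade 1-2 reddening on later days then has a place.
3. **Item 2b.** Provide separate entries for the pre-surgery and post-surgery imaging sessions. State how the RTOG grade relates to the CTCAE grade, or that it is reported separately.
4. **Section 10.1 and SAP 7a.** State that erythema is tabulated by grade and imaging session with an exact binomial interval, among patients who received MSOT readings.

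Cost: edits to one form and a few paragraphs, slightly more data entry, and a higher mild-event count. For patients already scanned, item 2b can be summarised with a note that its session may be unknown. The pooled estimate, its limits and the sample size stay as they are.

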STATISTICAL ANALYSIS PLAN

A Feasibility Study for the use of Multispectral Optoacoustic Tomography in the Detection of Solid Tumors and Lymph Nodes (MSOT)

Version date: June 29, 2022

IDE Number: G180105
NCT Number: NCT04365413
Sponsor: The University of Oklahoma Health Sciences Center
Stephenson Cancer Center
[name]
[name]
Principal Investigator: [name]
Professor
Stephenson Chair Cancer Imaging
Department of Surgery
University of Oklahoma Health Sciences Center
Stephenson Cancer Center
[name]
[name]
[contact]
Biostatistician
SAP Author: [name]
[name]

Abbreviations

CI	Confidence interval
FDA	Food and Drug Administration
IDE	Investigational Device Exemption
MSOT	Multispectral optoacoustic tomography
SAP	Statistical analysis plan

Contents

1. Objectives.....	4
a. Primary Objectives.....	4
b. Secondary Objectives.....	4
3. Design information	4
a. General statistical considerations.....	4
b. Sample Size and Power	4
4. Study Populations	5
a. Inclusion Criteria	5
5. Analysis Populations	5
6. Summary of Study Population	5
a. Patient Disposition.....	5
7. Safety Analyses	5
a. Adverse Events.....	5
8. Handling of Missing Data	6

1. Objectives

a. Primary Objectives

- i. To collect safety data on patients in whom MSOT was used to image tumor or lymph nodes
- ii. To evaluate skin temperature pre and post imaging (pre- and post-surgery) as part of the safety evaluation of MSOT

b. Secondary Objectives

- i. To detect tumor or lymph node by MSOT before and after surgical removal
- ii. To determine tumor positivity based on tissue pathology and detection of oxy- and deoxy-hemoglobin using MSOT localization
- iii. To determine tumor volume by MSOT before and after surgical resection

2. Study Endpoints

a. Primary Endpoint

- i. Adverse events as characterized by CTCAE v5.0 in patients that may result from MSOT imaging ($\geq 44^{\circ}\text{C}$)
- ii. Measurement of skin temperature pre- and post-MSOT imaging (pre- and post-surgery 4 measurements total) with a touch thermometer as part of the safety evaluation of the MSOT device. The thermometer will be placed onto the skin until a temperature appears, about 1 minute, and the temperature will be recorded.

b. Secondary Endpoints

- i. Tumor positivity as based on standard clinical laboratory techniques and signal detection of oxy- and deoxy-hemoglobin using MSOT localization
- ii. Identification of tumor and/or lymph nodes based upon either Isosulfan Blue or IC Green dye

3. Design information

a. General statistical considerations

This IDE FDA approved study will involve the interaction with patients that are scheduled for routine standard of care surgery. It will be a single-arm study that is designed to provide safety information regarding the use of the Acuity MSOT device in the clinical setting and the ability of MSOT imaging data to correlate with clinical findings identified via pathology.

b. Sample Size and Power

Study will initially accrue 10 patients for safety analysis regarding the use of the MSOT device pre- and post-surgery. If there are no grade III-V AEs observed in the patients as defined in CTCAE v5.0 per Section 8.2, we will submit an IDE supplement to request an enrollment expansion for an additional 40 patients, for a total of 50 patients. Up to an additional 55 patients will be accrued (to account for patient dropouts) to enroll 40 patients.

4. Study Populations

Inclusion and exclusion criteria are sometimes modified during the duration of the protocol. Before beginning analysis, the statistical team will review the criteria in the SAP to confirm it is up to date with the current criteria.

a. Inclusion Criteria

- i. Patients with an identified solid tumor, i.e. breast (Stage I-IV), melanoma (Stage I-IV), HNSCC (Stage I-III), pancreatic (Stage I-III), ovarian (Stage I-IV) that is scheduled for surgical removal of the tumor and completed standard imaging prior to surgery
- ii. Have acceptable hematologic status [total hemoglobin (tHb) \geq 10 mg/dL]
- iii. Patients \geq 18 yrs of age
- iv. Patient provided a signed and dated informed consent
- v. Willing to comply with study procedures and be available for the duration of the study
- vi. Ability to understand and the willingness to sign an IRB-approved informed consent document.

b. Exclusion Criteria

- i. Patients with central nervous system tumors
- ii. Patients with a tattoo over the surgical site
- iii. Pregnant women
- iv. Women who are breastfeeding
- v. Systemic or local infection
- vi. Any systemic anomaly during the pre-op assessment preventing patient participation in the study
- vii. Any febrile illness that precludes or delays participation preoperatively
- viii. Anything that would put the participant at increased risk or preclude compliance with the study
- ix. Patients with Stage IV pancreatic cancer, Stage IV HNSCC are not surgical candidates and therefore excluded from this study

5. Analysis Populations

- **Safety population:** All subjects who received MSOT readings will be included in the overall safety analysis, with toxicities graded according to NCI CTCAE v5.0. This is primarily a safety analysis study.

6. Summary of Study Population

a. Patient Disposition

- i. Descriptive statistics on the demographics and presenting features will be calculated. Proportions will be calculated for categorical variables and medians with the minimum and maximum will be calculated for continuous variables.

7. Safety Analyses

a. Adverse Events

- i. The severity of the AE will be graded by the Investigator using the NCI CTCAE, version 5.0.
- ii. The adverse events will be estimated by grade, type and relatedness. The first analysis will pool all grade 3 unexpected events that are possibly, probably or

definitely related to MSOT together and then construct a 95% exact Clopper-Pearson binomial confidence interval for this estimate.

b. Temperature Analysis

- i. Measurement of skin temperature will be evaluated where skin temperature greater than 44°C will be recorded and a 95% exact Clopper-Pearson binomial confidence interval constructed.

c. Secondary Analysis

- i. Tumor positivity from pathology reports and MSOT readings will be compared and Pearson correlation coefficient created.
- ii. Deoxy- and oxy-genation levels will be compared to non-tumor values from the same patient. Paired t-tests will be used to compare the values and a Wilcoxon Signed Rank test performed. Median and interquartile range will be reported.

8. Handling of Missing Data

Every effort will be made to collect information at all defined visits including at early withdrawal or dropout. Reasons for missing data will be summarized. However, there will be no imputation of missing data.

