10.2 Analysis of Secondary Objective

10.2.1 There are three secondary outcomes of interest, two of these will be based upon a positivity (yes/no) (secondary outcomes 1 and 3) and one of these will assess on a continuous scale tumor size/ volume (secondary outcome 2). In each of these analyses, we will compare the information gathered from the MSOT approach (size, positivity tumor (yes/no), positivity of dye (yes/no)) for each patient and then compare these measures to those that are available from information gathered in the standard of care approach (i.e., from pathology reports after resection).

For continuous outcomes we will examine three characteristics based on comparing the MSOT and standard of care (“gold standard”) assessments. These include: 1) the mean difference in the measure (i.e., tumor volume or size), 2) the correlation between the measures taken using MSOT or standard of care; and 3) the comparison of variability of the measures from the two approaches (MSOT and standard of care). For the first approach we will calculate a paired t-test, for the second we will estimate a Pearson correlation and for the third we will perform an F-test to compare the equality of variances. With the expanded sample size of 50 patients we can detect a difference in values of volume (or size) equal to 0.4 standard deviations or less of the measure of difference in tumor volumes (or size) with 80% power using a paired t-test with $\alpha=0.05$ (2-sided). In addition, there is 80% power to detect a correlation of 0.38 (or larger) with an $\alpha=0.05$ (2-sided). Finally, there is 80% power to detect a ratio of 2.24 (or larger) when comparing variances between the two groups (note: this ratio corresponds to a ratio of 1.5 on the standard deviation scale).

If the study is terminated early with 45 patients scanned, we can still detect a difference in values of volume (or size) equal to 0.43 standard deviations or less of the measure of difference in tumor volumes (or size) with 80% power using a paired t-test with

alpha=0.05 (2-sided). In addition, there is 80% power to detect a correlation of 0.40 (or larger) with an alpha=0.05 (2-sided). Additionally, there is 80% power to detect a ratio of 2.35 (or larger) when comparing variances between the two groups (note: this ratio corresponds to a ratio of 1.53 on the standard deviation scale)

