For binary outcomes (positivity and presence of dye), we will estimate the MSOT approach and the corresponding 95% Clopper-Pearson exact binomial confidence interval. Accuracy is defined as the number of patients where the MSOT and standard of care approach are in agreement (i.e., both are positive or both are negative). In addition, we can examine other characteristics of the two approaches including sensitivity, specificity, positive predictive value and negative predictive values.

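### SAP 7.c.i names only a Pearson correlation for tumour positivity, a yes/no endpoint for which Protocol 10.2 sets an agreement analysis with an exact interval that the SAP does not carry over

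*SAP*

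**What the plan says.** Protocol 10.2 sorts the three secondary outcomes by scale: "two of these will be based upon a positivity (yes/no) (secondary outcomes 1 and 3"), while outcome 2, tumour size or volume, is continuous. Section 6.2 shows that outcome 1 is tumour positivity and outcome 3 is identification by dye. Section 10.2 lists positivity as yes/no among the MSOT measures, and Appendix A records positive tumour tissue as Yes or No.

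For the continuous outcome, 10.2 names a paired t-test, a correlation and an F-test: "for the second we will estimate a Pearson correlation". For the others it states: "For binary outcomes (positivity and presence of dye), we will estimate the MSOT approach and the corresponding 95% Clopper-Pearson exact binomial confidence interval". It continues: "Accuracy is defined as the number of patients where the MSOT and standard of care approach are in agreement". Sensitivity, specificity and the predictive values come in more loosely: "In addition, we can examine other characteristics of the two approaches".

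SAP 7.c.i gives positivity a different treatment: "Tumor positivity from pathology reports and MSOT readings will be compared and Pearson correlation coefficient created". Item 7.c.ii then compares oxygenation levels with non-tumour values. Clopper-Pearson intervals appear in the SAP only for adverse events (7.a.ii) and skin temperature (7.b.i). SAP 2.b.ii lists a dye endpoint, "Identification of tumor and/or lymph nodes based upon either Isosulfan Blue or IC Green dye", for which 7.c gives no analysis.

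**The concern.** The two documents give different methods for the same endpoint, and neither says which prevails. An analyst working from the protocol would report the proportion of patients in whom MSOT and pathology agree, with an exact interval. An analyst working from SAP 7.c.i has one named statistic, a correlation coefficient, and no interval.

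A correlation does not tell the reader how often MSOT gave the same answer as pathology. It also needs variation in both variables. Everyone enters with an identified solid tumour (Protocol 4.1.1), so pathology-negatives may be few, and that is where the coefficient becomes unstable or fails. At stake is whether the secondary result on tumour detection can be interpreted.

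**Working it through.** **The plan's own Pearson figure.** The only figure attached to a Pearson correlation is in Protocol 10.2, for volume or size: 80% power for r = 0.38 with 50 patients and for r = 0.40 with 45, two-sided alpha 0.05. Fisher's z approximation gives power = Φ(atanh(r)·√(n−3) − 1.96).

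- n = 50: Φ(0.4001 × √47 − 1.96) = Φ(0.783) = 78.3%.
- n = 45: Φ(0.4236 × √42 − 1.96) = Φ(0.786) = 78.4%.

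Both are within two points of 80%, so that figure stands. No figure is given for positivity.

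**What Pearson becomes on yes/no data.** Let TP, FN, FP and TN count MSOT calls against pathology. Pearson r is then phi:

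r = (TP·TN − FN·FP) / √[(TP+FN)(FP+TN)(TP+FP)(FN+TN)].

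If any margin is zero the denominator is zero and r does not exist. Accuracy as Protocol 10.2 defines it is (TP+TN), here taken over N.

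**A perfect result.** If all 50 patients are positive on both, TP = 50 and the other cells are 0, so r is undefined. The protocol's analysis gives 50/50 = 100%, with exact lower limit 0.025^(1/50) = 92.9%, so CI 92.9% to 100%.

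**Agreement held at 45/50.** The number of patients is from the protocol. The 45 agreements, the number of pathology-negatives and the error splits are assumptions. Exact limits for 45/50 are the 2.5% quantile of Beta(45, 6) and the 97.5% quantile of Beta(46, 5): 78.2% to 96.7%. That result is the same in every row. The range for r covers every split of the five errors between missed tumours and false positives.

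| Pathology-negatives | Table giving lowest r (TP/FN/FP/TN) | Table giving highest r | Range of r |
|---|---|---|---|
| 25 | 22/3/2/23: 500/√(25·25·24·26) = 0.80 | 20/5/0/25: 500/√(25·25·20·30) = 0.82 | 0.80 to 0.82 |
| 10 | 39/1/4/6: 230/√(40·10·43·7) = 0.66 | 35/5/0/10: 350/√(40·10·35·15) = 0.76 | 0.66 to 0.76 |
| 5 | 44/1/4/1: 40/√(45·5·48·2) = 0.27 | 40/5/0/5: 200/√(45·5·40·10) = 0.67 | 0.27 to 0.67; undefined for 45/0/5/0 |
| 0 | 45/5/0/0: zero margin | none | undefined |

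Sensitivity and specificity change between these tables, so the spread is not an effect of prevalence alone. The table shows only that one agreement rate is compatible with very different values of r.

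**If the readings are numeric.** Appendix B records haemoglobin signals as values, so *MSOT readings* could mean a number. The coefficient would then be point-biserial and the table would not apply. It would still not be the yes/no comparison in Protocol 10.2.

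**The case against.** Four points on the other side deserve weight.

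- **Phi is a legitimate statistic, and the study aims to correlate.** SAP 3.a refers to "the ability of MSOT imaging data to correlate with clinical findings identified via pathology". This is true, so a reader who infers that Pearson is invalid on binary data goes too far. The fault is that it is not the quantity the protocol set for this endpoint.
- **The SAP also says positivity will be compared, and nothing in it withdraws the protocol's analysis.** The two texts can be read as additive, and a reader should not infer that the agreement analysis was deliberately dropped. But an unnamed comparison specifies no method, and the only method named is the correlation.
- **The coefficient may well exist.** It is tempting to conclude that it will be undefined in this trial. The documents do not support that: no negative rate is stated, and lymph-node targets, neoadjuvant cases (Appendix A records both) or post-surgery images may supply negatives. With 10 to 25 negatives the movement in r is moderate.
- **The protocol text is itself incomplete.** It says the MSOT approach will be estimated without naming the quantity. Applying the exact interval to accuracy is an inference from the definition that follows directly after it. The inference is natural, but the sentence should be repaired too.

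**Conclusion.** The mismatch holds. SAP 7.c.i names only a Pearson coefficient for an endpoint that Protocol 10.2 treats as yes/no, and the protocol's agreement analysis and any dye analysis are absent from SAP 7.c. That conclusion rests on the text and needs no assumption about the data.

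The size of the numerical consequence does rest on assumptions: yes/no readings, 50 patients, 45 agreements and a chosen number of negatives. Under these, r for the same 90% agreement can be as high as 0.82 or as low as 0.27, or can fail to exist.

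The SAP calls this primarily a safety study. The adverse-event and temperature analyses do not use this coefficient, so no inference about the safety conclusion is warranted.

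**What to change.** In SAP 7.c.i, replace Pearson for positivity with the protocol's binary analysis. Suggested wording:

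> *MSOT tumour positivity (yes/no, by a rule fixed before analysis) will be cross-tabulated against pathology. Agreement will be reported as n/N with a 95% Clopper-Pearson confidence interval. Dye positivity will be analysed in the same way.*

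- **Further accuracy measures.** Sensitivity, specificity, PPV and NPV are recommended as n/N with exact 95% intervals, or as not estimable when the denominator is zero. Making them mandatory goes beyond the protocol, which only allows for them. Agreement, PPV and NPV depend on prevalence and should be read beside sensitivity and specificity.
- **Definitions.** Say what *MSOT readings* means, what rule makes a reading positive, and which scan is compared with pathology, given that objective 3.2.1 covers imaging before and after removal. Neither document defines the rule or the scan, so copying the protocol text will not settle them.
- **Volume.** Pearson belongs to the protocol's volume/size analysis. The SAP has no such analysis, although volume is its objective 1.b.iii. If it is to be done, carry it over from Protocol 10.2.
- **Protocol 10.2.** Complete the sentence so that it names accuracy as the quantity estimated.

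The cost is SAP and protocol wording and slightly more analysis work, with no new patients or scans. One downside is that a wide or absent specificity interval may become visible.
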